8.1.9 Use of an Efficacy Subset of Subjects

Subjects randomized to study drug who were dispensed study product and do not have major protocol deviations will form the Per Protocol (PP) Population. The requirements for the PP Population are outlined in Section 8.4.4. Any additional major protocol deviations will be defined at the time of evaluability evaluation, the time between the database soft lock and hard lock before unblinding.

Excluding subjects who have major protocol deviations will decrease the variability in treatment response and will allow for a better determination of dose-response relationship of S5G4T-1, E-BPO Cream, 5%.

8.1.10 Active-Control Studies Intended to Show Equivalence

Not applicable to this study.

8.1.11 Examination of Subgroups

Subset analyses will be conducted for the ITT populations for the subgroups based on at least the following:

- Baseline Global Severity;

- Categorized as Baseline IGA = 3 (moderate) and Baseline IGA = 4 (severe); due to the inclusion criteria requiring subjects to have either a 3 or 4 IGA score at study entry other IGA response categories will not be presented
- Sex;
 - Male versus female subjects
- Age;
 - Dichotomized to less than the median age of ITT subjects and greater than or equal to the median age of ITT subjects
- Ethnicity;
 - Categorized as Hispanic or Latino and Not Hispanic or Latino; ethnicities of Not Reported and Unknown will not be included
- Race
 - Categorized as White and Non-White; subjects indicating more than one race category which includes both white and a non-white race will be summarized under the Non-White subgroup.

Subset analyses will be conducted on the variables absolute change from Baseline in inflammatory lesions at Week 12 as well as the dichotomized global severity score at Week 12. These analyses will contain only descriptive statistics.

8.2 Disposition of Subjects

The number of subjects included in each analysis population (randomized, ITT, Safety, and PP) will be summarized by treatment group and overall. The number of subjects completed and discontinued (including the reasons for discontinuation) will be summarized for each treatment group as well as by overall. The percentages will be calculated based on the number of randomized patients, unless otherwise specified.

8.3 Protocol Deviations

In order to define the PP Population, protocol deviations potentially influencing the evaluation of the primary efficacy endpoint will be defined as major deviations. The protocol deviations that will exclude a subject from PP are given in Section [8.4.4](#).

In case other deviations detected during the study conduct are considered to potentially influence the evaluation of the primary efficacy endpoint, these deviations will be documented prior to the database lock and the patients having these deviations will be excluded from the PP Population.

All protocol deviations will be reported to the sponsor and recorded throughout the study. Protocol deviations will not be entered into the database. SolGel will provide a list of protocol deviations to QST. A tabulation of protocol deviations will be presented in a data listing.

8.4 Data Sets Analyzed

Subjects will be presented/summarized based on the primary reason for exclusion. Below is the order to be used in summaries:

8.4.1 Randomized Population

All subjects who are randomized to study treatment will be included in the randomized population and will be analyzed according to the treatment group they were randomized. Listings will be provided for all randomized subjects.

8.4.2 Intent-to-Treat (ITT) Population

All subjects in the randomized population who are dispensed study product will be included in the ITT population and will be analyzed according to the treatment group they were randomized. All efficacy analyses will be presented using the ITT population.

8.4.3 Safety Population

All subjects in the randomized population who are presumed to have used the study product at least once and who provide at least one post-baseline safety evaluation will be included in the Safety population and will be analyzed according to the treatment they received. Presumed to have used study product will be defined as having at least one confirmed application of study medication. All safety analyses will be performed using the Safety population.

8.4.4 Per-Protocol (PP) Population

All subjects in the ITT population who complete the Week 12 evaluation without noteworthy study protocol violations (i.e., any patient or investigator activity that could have possibly interfered with the therapeutic administration of the treatment or the precise evaluation of treatment efficacy) will be included in the PP population and analyzed according to the treatment group they received. The PP population will include subjects in the ITT population who do not meet any of the following criteria:

- Failed any of the inclusion/exclusion criteria;
- Have taken any interfering concomitant medications;
- Did not attend the Week 12 Visit;
- Missed more than 1 post-baseline study visit prior to Week 12;
- Have not been compliant with the dosing regimen (i.e., Patients may not miss more than five consecutive days of dosing and must take 80 to 120% of expected applications. The number of expected applications will be determined for each patient based on the length of their participation in the study);
- Out of visit window (± 4 days) at the 12-week Visit.

Subjects that discontinue from the study due to an AE related to study treatment or documented lack of treatment effect will be included in the PP population. Data for these subjects will not be imputed by multiple imputation but rather their data will be imputed with values consistent with their status as treatment failures. See Section 8.1.5 for additional detail. Prior to breaking the blind, other additional criteria may be added to the list to accommodate for unforeseen events that may occur during the conduct of the trial and result in noteworthy study protocol violations.

All efficacy analyses performed on the PP population will be according to the treatment they received.

8.5 Demographic and Other Baseline Characteristics

All Baseline summaries will be done on the ITT, PP, and Safety populations by treatment group and overall.

Sex (categorical), race (categorical), and ethnicity (categorical) will be summarized by counts and percentages. Age (continuous), height (cm) (continuous), and weight (kg) (continuous), and body mass index (BMI) (continuous) will be summarized with descriptive statistics.

Age will be calculated as the difference in days between the date of birth and the date of informed consent and converted to years by dividing the number of days by 365.25 and using a floor function to drop the decimal portion. In case the exact birth day is missing, day 15 will be used. The BMI will be calculated as weight (kg) divided by squared height (m^2).

Medical histories will be coded using the Medical Dictionary for Regulatory Activities (MedDRA) dictionary and presented in a by-subject listing.

The medical history data will be summarized with frequencies and percentages of patients with at least one medical history term reported, and patient frequencies and percentages on the System Organ Class (SOC) and Preferred Term (PT) levels. The number of events will also be summarized. The table will be sorted by overall descending frequency of SOC and then, within a SOC, by overall descending frequency of PT.

8.6 Prior and Concomitant Medications

Concomitant medications will be coded to preferred name and Anatomical Therapeutic Chemical (ATC) classification of ingredients using the World Health Organization (WHO) Drug Global Dictionary, Format B3, Version March 1, 2018.

Medications which start prior to first application will be considered prior medications. Ongoing medications and medications ending after the date of first application will be considered concomitant medications. If the date of first application is unknown and the medication is not listed as ongoing the interval will be considered “unknown”. If the date of first application is unknown and the medication is listed as ongoing the interval will be considered concomitant.

Incomplete medication start and end dates will be imputed as described in Section [8.1.5.3](#)

A summary of prior and concomitant medications will be provided.

A by-subject listing of all prior and concomitant medications will be presented for the Safety population.

8.7 Analysis of Efficacy

Inflammatory lesion counts will be summarized at each evaluation from Baseline through Week 12. Absolute and percent change in lesion counts will be summarized at Weeks 2, 4, 8, and 12. IGA scores will be summarized from Baseline through Week 12 using descriptive statistics. The dichotomized IGA scores will be summarized at Weeks 2, 4, 8, and 12 using descriptive statistics.

All efficacy results will be presented in by-subject listings.

8.7.1 Primary Efficacy Analysis

The primary efficacy analysis will be presented on both the ITT and PP populations.

8.7.1.1 Lesion Counts

Tests of superiority for the absolute change from Baseline in inflammatory lesions will be based on either parametric or non-parametric methods consistent with the statistical assumptions required to support the analyses. Specifically, the tests of superiority will be based on an ANCOVA with factors of treatment and analysis center and the respective Baseline lesion count as a covariate or on ranked data submitted to an ANCOVA with factors of treatment and analysis center and the respective Baseline lesion count as a covariate. If the treatment-by-analysis center interaction effect is significant at an alpha less than 0.10, then the effect will be included in the model; otherwise it will be removed.

A skewness test, based on the methods presented by J.H. Zar [4], will be applied to the residuals resulting from an ANCOVA. A two-sided p-value for the skewness test significant at 0.01 will imply the use of the non-parametric method. If a parametric analysis is indicated, the results of the parametric analysis will be considered the primary analysis. Should a non-parametric analysis be indicated, the absolute or percent changes in inflammatory lesions will be rank transformed prior to submitting them to the ANCOVA. Results of the rank-transformed analyses then will be considered the primary analysis; however, results of the non-ranked transformed analyses will also be presented.

The following steps provide a brief synopsis of the process that will be followed.

1. Missing data will be imputed using multiple imputation. Refer to Section 8.1.5.1.
2. The pooling analysis will be conducted. Refer to Section 8.1.7.
 - a. The treatment-by-analysis center interaction p-values from both parametric and non-parametric (unranked and ranked) analyses will be presented, along with the skewness p-value calculated from the residuals from the unranked ANCOVA. The skewness p-value will determine which analysis results to report:
 - i. Skewness p-value > 0.01 : Report results based on the parametric (unranked) approach.
 - ii. Skewness p-value ≤ 0.01 : Report results based on the non-parametric (ranked) approach.
3. For the primary efficacy analysis
 - a. Results of both parametric and non-parametric (unranked and ranked) analyses will be presented. For each, data will be submitted to an ANCOVA with factors of treatment and analysis center and Baseline lesion count as a covariate (if the

treatment-by-analysis center interaction p-value is ≤ 0.10 , the interaction will also be included in the model). The residuals from the unranked analysis will be used to calculate the skewness p-value. The skewness p-value will determine which analysis results to report:

- i. Skewness p-value > 0.01 : Report results from the parametric (unranked) ANCOVA.
 - ii. Skewness p-value ≤ 0.01 : Report results from the non-parametric (ranked) ANCOVA.
4. If there was a significant treatment by analysis center interaction (as determined in step 1 – the pooling analysis), a sensitivity analysis will be performed as described in Section 8.1.7 to find the extreme analysis center(s). Then step 3 above will be repeated the extreme analysis center(s) removed, to confirm the treatment response.

8.7.1.2 Investigator Global Assessment (IGA)

The IGA will be dichotomized into “success” and “failure” with a patient considered a success for those visits if the IGA is “clear” or “almost clear”. The analysis of the dichotomized IGA will be based on a logistic regression test with factors of treatment group and analysis center.

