8.1.4 Adjustments for Covariates

Baseline lesion count will be a covariate for the primary efficacy endpoint for lesion counts. No other covariates are planned to be used in the analyses for this study.

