8.1.5.2 IGA Missing Data Imputation

A similar procedure will be used for the analyses based on proportion of IGA successes wherein the ANCOVA analysis is replaced with a logistic regression analysis. Specifically, missing IGA values from which the dichotomized IGA is derived will be estimated by MCMC.

The pattern of missing observations in each treatment group cannot influence the missing value estimation in the other because the imputation is being conducted independently for each treatment group.

The missing IGA values will be derived for the analysis using the method of MCMC multiple imputation. Multiple imputation and subsequent analysis will involve 3 principal tasks:

1. Create a data set, one for each treatment group, of patients with observed values and those needing estimation by MCMC. The missing IGA values in each data set will be filled in using the MCMC method 5 times to generate 5 data sets. The resulting data sets for each treatment arm will be combined into one complete data set by imputation.

Syntax:

```
proc mi data=datain out=dataout seed=&seed. nimpute=5 <options>;  
  where trtpn=(1, or 2);  
  mcmc chain=multiple;  
  var baseline week2 week4 week8 week12;  
run;
```

2. For each complete data set, the dichotomous success rate (clear or almost clear) will be computed. The estimated global values will be rounded to the nearest integer value prior to evaluating the success rate. Each complete data set will be analyzed with a logistic regression with factors of treatment group and analysis center.
3. The results from these analyses will be combined into a single inference using SAS PROC MIANALYZE.

A total of 2 random seeds will be needed to impute IGA for the two treatment groups. Those 2 random seeds have been pre-specified by using a random number generator:

- IGA Week S5G4T-1: Seed = 712066910
- IGA Week Vehicle: Seed = 1200150465

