The consistency of treatment response will be investigated across the analysis centers subsequent to combining the data as described above. Statistical tests will be conducted to identify if there are extreme analysis centers that could affect the interpretation of common statistical and clinical conclusions. An analysis center by treatment interaction will be included in the primary analyses to test for parallel treatment effect at an alpha level of 0.10. Change from Baseline in inflammatory lesions will be analyzed with an ANCOVA (unranked or ranked) with factors of treatment group, analysis center, and treatment group by analysis center interaction, and the Baseline lesion count variable as a covariate. For the purpose of testing consistency of treatment response, the dichotomized IGA will be analyzed with a logistic regression with factors of treatment group, analysis center, and the interaction term of treatment group by analysis center. Further examination will follow for any variables that have a significant ANCOVA or logistic regression interaction term.

In the event that the ANCOVA or logistic regression interaction (referred to henceforth as the “appropriate test”) p-value is less than or equal to 0.10, a sensitivity analysis that excludes analysis centers with the extreme efficacy result will be performed to determine the robustness of the treatment effect. On the other hand, if all three analyses result in interaction terms with p-values greater than 0.10, then the conclusions from the pooled data will be considered to be free of the impact of extreme analysis centers.

The first step in conducting a sensitivity analysis is to identify the extreme analysis center or centers that contribute to the statistical significance of the appropriate test. The process involves submitting subsets of analysis centers to the appropriate test and observing the appropriate test p-value for the subset. Subsets with p-values greater than 0.10 for the appropriate test are considered homogeneous.

The search for an extreme analysis center begins by analyzing all subsets that can be created by excluding one analysis center. If one or more of the subsets result in an appropriate test p-value greater than or equal to 0.10, then the analysis center excluded from the subset with the largest p-values for the appropriate test is deemed to be the extreme analysis center.

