8.7.2.2 Sensitivity Analyses for IGA

The first sensitivity analysis for the dichotomized IGA success will use a repeated measures logistic regression model (generalized estimating equations), with dichotomized IGA success as the dependent variable and treatment, analysis center, visit (i.e., Weeks 2, 4 and 8), and treatment group by visit interaction as independent factors. In this analysis, data from all post-baseline visits will be included with no imputation for missing data.

The second sensitivity analysis will use the model based multiple imputation method to impute missing data for the dichotomized IGA data. The multiple imputation will involve 3 principal tasks:

1. Missing values will be filled in 5 times to generate 5 complete data sets. The imputation model used logistic regression with factors of treatment group and analysis center (i.e., the imputation model will be the same as the analysis model).

Syntax:

```
proc mi data=datain out=dataout seed=&seed. nimpute=5 <options>;  
  class trtpn sitegr1 diiga;  
  var trtpn sitegr1 diiga;  
  monotone logistic (sitegr1=trtpn);  
  monotone logistic (diiga=trtpn sitegr1);  
run;
```

2. Each complete data set will be analyzed with a logistic regression a factors of treatment group and analysis center.
3. Results from these analyses will be combined into a single inference.

One random seed will be needed to impute IGA. The following random seed has been pre-specified by using a random number generator:

IGA Seed= 184392230

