8.7.4 Supportive Efficacy Analysis

Appropriate descriptive statistics will be computed for all supportive efficacy parameters.

In addition, the mean change comparison in PAPSS item 1 (burning), item 2 (itching), item 3 (redness) and item 4 (bumps) from Baseline to Week 12 will be analyzed using an analysis of variance (ANOVA) with factors of treatment, analysis center, and the respective Baseline score. Missing values will not be imputed.

A set of cumulative distribution function curves will be generated to allow for the evaluation of within-person change by treatment group. Specifically, 5 plots will be generated showing the change from Baseline to Week 12 (and/or other, earlier time points if so desired) by the cumulative percent of subjects for each of the treatment arms (change on the x-axis will be expressed as absolute change) on:

- PAPSS total scale scores

- The total scale score is the sum of PAPSS items 1 through 4.
 - PAPSS item 1 (burning) scores
 - PAPSS item 2 (itching) scores
 - PAPSS item 3 (redness) scores
 - PAPSS item 4 (bumps) scores

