9. DETERMINATION OF SAMPLE SIZE

The following power calculations are based on the observed Week 12 results of the Phase 2 study, SGT-EBP01-09. This study was a three-arm trial including E-BPO cream, 1% and 5%, and vehicle in the treatment of rosacea. Estimates from the E-BPO cream, 5% arm were used in the power assessments. The anticipated randomization ratio is 2:1 for E-BPO cream, 5% and vehicle, respectively. The computations were performed with nQuery Advisor Version 7.0 using a two-sided test with a statistical significance value of 0.05.

A sample size of 86 in the E-BPO cream, 5% and 43 in the vehicle group has 95% power to detect a statistically significant difference in the proportion of patients who have at least a 2-grade reduction at Week 12 from Baseline in IGA and are clear or almost clear. The estimated percentages with a 2-grade reduction at Week 12 from Baseline in the IGA and clear or almost clear are 53.3% and 20.0% for the E-BPO cream and vehicle, respectively.

A sample size of 200 in the E-BPO cream, 5% and 100 in the vehicle group has 95% power to detect a statistically significant difference in inflammatory lesions. The estimated absolute change from Baseline in treatment means were -14.1 and -7.4 for E-BPO cream and vehicle, respectively, with a standard deviation (SD) of 6.70 and 17.24, respectively.

The sample sizes above will be increased to give a planned enrollment of 234 in the E-BPO cream, 5% group and 117 in the vehicle group since the Phase 3 trial is expected to enroll patients who are as a group more severe than those of the Phase 2 trial. This is a consequence of some changes in the inclusion criteria.

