^c Skewness test, based on methods presented by J.H. Zar (1984), assessed for each imputed dataset. The average p-value is presented.

^d P-value for the interaction term from a logistic regression with factors of treatment, investigational site, treatment by investigational site interaction.

^e P-value for the interaction term from a ranked analysis of covariance with factors of treatment, analysis center, treatment by analysis center interaction and Baseline lesion count as a covariate.

^f P-value for the interaction term from an unranked analysis of covariance with factors of treatment, analysis center, treatment by analysis center interaction and Baseline lesion count as a covariate.

^g P-value for the interaction term from a logistic regression with factors of treatment, analysis center, treatment by analysis center interaction.

Note: Multiple imputation (MCMC) used to impute missing values.

SOURCE: USERNAME/SPONSOR/PROJECT/JOBNAME (DATE,TIME)

{NOTE TO PROGRAMMER: ADJUST FOOTNOTE “d” AND/OR “g” IF FIRTH’S PENALIZED LIKELIHOOD IS NEEDED}

Table 14.2.1.2: Primary Efficacy Analysis: Absolute Change from Baseline in Inflammatory Lesion Count and Dichotomized IGA Success at Week 12 (Intent-to-Treat Population)

	E-BPO 5% Cream (N=xxx)	Vehicle Cream (N=xxx)	Skewness P-Value	Treatment P-Value
Inflammatory Lesion Count – Absolute Change from Baseline				
LSMean ^a	xx.x	xx.x	x.xxx ^b	x.xxx ^a
LSSD ^a	xx.xx	xx.xx		x.xxx ^c
Achieving Clear or Almost Clear				
Success	xx.x%	xx.x%	N/A	x.xxx ^d
Failure	xx.x%	xx.x%		

^a Least squares means, standard deviations and treatment p-value from an analysis of covariance with factors of treatment group and analysis center and Baseline lesion count as a covariate. Negative least squares means values represent decrease from Baseline.

^b Skewness test, based on methods presented by J.H. Zar (1984), assessed for each imputed dataset. The average p-value is presented.

^c P-value from a ranked analysis of covariance with factors of treatment group and analysis center and Baseline lesion count as a covariate.

^d P-value from a logistic regression with factors of treatment group and analysis center.

Note: Multiple imputation (MCMC) used to impute missing values.

SOURCE: USERNAME\SPONSOR\PROJECT\JOBNAME (DATE, TIME)

{NOTE TO PROGRAMMER: ADJUST FOOTNOTE “d” IF FIRTH’S PENALIZED LIKELIHOOD IS NEEDED}

Repeat Table 14.2.1.2 for the following table:

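### The IGA co-primary model omits baseline IGA grade (3 or 4): the test is valid, but if the true effect is well below plan, chance imbalance in severity shifts the verdict, which one prespecified term would largely prevent

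*SAP*

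**What the plan says.** SAP 8.7.1.2, in line with protocol 19.4.2: "The analysis of the dichotomized IGA will be based on a logistic regression test with factors of treatment group and analysis center". SAP 8.1.4 names baseline lesion count as the covariate for the lesion-count endpoint and adds: "No other covariates are planned to be used in the analyses for this study".

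The same two-factor model runs through the IGA analyses:
- after multiple imputation (8.1.5.2, step 2): "Each complete data set will be analyzed with a logistic regression with factors of treatment group and analysis center";
- in the table footnotes: "P-value from a logistic regression with factors of treatment group and analysis center";
- in the model-based imputation (8.7.2.2): "The imputation model used logistic regression with factors of treatment group and analysis center";
- with an interaction added, in the check of consistency across centers (8.1.7): "the dichotomized IGA will be analyzed with a logistic regression with factors of treatment group, analysis center, and the interaction term";
- by reference, in the Week 8 and Week 4 secondary tests (8.7.3).

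Other endpoints do adjust for their own baseline. The lesion-count ANCOVA (8.7.1.1) includes baseline count, and the PAPSS items (8.7.4) use an "analysis of variance (ANOVA) with factors of treatment, analysis center, and the respective Baseline score". The PAPSS model already makes the blanket sentence in 8.1.4 inaccurate.

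Baseline IGA is used in the MCMC imputation variable list (8.1.5.2), in Table 14.1.2.1 and in a descriptive subgroup (8.1.11). Randomization is stratified by site only (protocol 12.1).

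**The concern.** Success is an end state, IGA 0 or 1. Every eligible patient starts at 3 or 4, so a severe patient has one grade further to travel. Baseline grade is therefore very likely prognostic. It is recorded for everyone, it is not balanced by design, and it is not in the model.

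Leaving it out is not an error: averaged over all randomizations the test keeps its level. In any one trial, however, the severe patients fall between the arms in one particular way, and the unadjusted test counts that as part of the treatment difference.

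The IGA test is also a gate. Under SAP 8.1.8, failure of either co-primary endpoint invalidates every secondary test, and secondary steps 3 and 5 use the same model. Table 14.1.2.1 and the subgroup summary would show an imbalance but would not correct the p-value.

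**Working it through.** **1. The plan's own figure.** SAP section 9: "The estimated percentages with a 2-grade reduction at Week 12 from Baseline in the IGA and clear or almost clear are 53.3% and 20.0" percent, with 86 active and 43 vehicle for 95% power, two-sided 0.05, 2:1.
- Average rate = (0.200 + 2 × 0.533)/3 = 0.422.
- Vehicle n without continuity correction = [1.96·√(1.5 × 0.422 × 0.578) + 1.645·√(0.160 + 0.2489/2)]² / 0.333² = (1.186 + 0.877)²/0.1109 = 38.4, so 39.
- With continuity correction: (38.4/4)·[1 + √(1 + 6/(38.4 × 2 × 0.333))]² = 42.8, so 43, and 86 active. The plan's figure reproduces.

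**2. Power at the planned 234/117, vehicle 20%** (normal approximation): over 99.99% at 53.3%, 84% at 35%, 66% at 32%, 52% at 30%.

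**3. Is a smaller effect plausible?** The planned rates come from Phase 2 arms of 30 to 32 patients (SAP section 4). Taking 30 per arm, the SE of the difference is √(0.533 × 0.467/30 + 0.2 × 0.8/30) = 0.117, so the 95% interval is 33.3 ± 22.9, about 10 to 56 points. Differences of 12 and 15 points lie inside it.

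**4. Size of chance imbalance.** SD of the between-arm difference in severe share = √(q(1−q)(1/234 + 1/117)) = 0.1132·√(q(1−q)). This gives 3.4 points at q = 10%, 4.5 at 20%, 5.2 at 30%, 5.4 at 35% and 5.5 at 40%.

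**5. Simulation A.** 351 patients and 28 sites: 12.5 per site, below the SAP minimum of 15, so pooled in pairs to 14 centers. Blocks of 3 within site, center SD 0.4 on the logit scale (assumed), no missing data, Wald test. The severe share (10–40%) and the odds ratio for moderate v severe (1, 2 or 4) are assumed.
- 53.3% v 20.0%: power 100% of 2,000 trials with either model.
- 20% v 20%: type I error 5.0–5.6% either way.
- 35% v 20%: average gain from the term nil (odds ratio 1), 0.1–0.6 points (2), 0.5–2.4 points (4); for example 84.9% to 87.1% at 30% severe, odds ratio 4. The paired Monte Carlo SE is at most 0.4 points.
- The SE of the log odds ratio does not shrink (0.278 without, 0.280–0.290 with). The gain is in test power.

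Power conditional on imbalance, 35% v 20%:

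| Severe share, odds ratio | Active >1 SD more severe: planned / with term | Active >1 SD less severe: planned / with term |
|---|---|---|
| 30%, 4 | 76% / 88% | 92% / 86% |
| 10%, 2 | 84% / 86% | 89% / 87% |

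Repeating the 30%, odds ratio 4 case with 13 centers gives 86% v 88% overall, 79% v 90% and 95% v 89%.

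**6. Simulation B**, imbalance fixed at about its 10th or 90th percentile. 13 centers of 18:9, center SD 0.3 (both assumed), 32% v 20%. The odds ratio is severe v moderate, so 0.3 corresponds to 3.3 in A's direction. Percentage of trials passing in favor of active, imbalance favoring active / none / against:

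| Severe share, odds ratio, imbalance | Planned model | With baseline IGA |
|---|---|---|
| 35%, 0.3, 6.8 points | 77.7 / 67.2 / 57.2 | 70.7 / 68.9 / 69.8 |
| 20%, 0.3, 5.8 points | 74.5 / 70.2 / 59.0 | 67.9 / 72.0 / 68.6 |
| 10%, 0.5, 4.3 points | 70.5 / 67.0 / 65.1 | 67.0 / 67.1 / 68.9 |

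The planned model swings by 20.5, 15.5 and 5.4 points from favorable to unfavorable. With the term, the range is at most 4.1 points and has no consistent direction.

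Under the null, overall type I error is 5.0–5.7% without and 5.0–5.9% with the term (simulation error about 0.4). Given an imbalance at 35% severe, odds ratio 0.3, the one-sided false-positive rate (nominal 2.5%) runs from 1.1% to 3.9% with the planned model and from 2.1% to 2.6% with the term.

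The term moves verdicts in both directions. At 35% v 20%, 35% severe, odds ratio 0.3, the models disagree in 4.1% of trials and power goes from 85.2% to 86.7%. So (4.1 + 1.5)/2 = 2.8% gain significance and (4.1 − 1.5)/2 = 1.3% lose it.

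**The case against.** The best defense is that treatment plus center, with randomization stratified by site, is a coherent prespecified analysis with the right type I error and nearly certain success at the planned effect. Every non-zero gain needs an effect under half of plan (15 v 33.3 points) plus a severe share and an association that the documents do not state. The average gain is at most 2.4 points. The same argument applies to any omitted prognostic factor. All of this stands, and it is why this is an efficiency choice and not an error.

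IGA is also not the limiting endpoint. If the lesion effect shrank in proportion, to 6.7 × 15/33.3 = 3.0 lesions, lesion-count power at 234/117 with the stated SDs (6.70 and 17.24) would be about 45% (unpooled variance) to 65% (pooled), before any gain from the covariate. If the endpoints were independent, a 2.4-point IGA gain would become 2.4 × 0.45 = 1.1 to 2.4 × 0.65 = 1.6 points of trial success. That limits the average benefit. It does not remove the dependence of the IGA verdict on imbalance.

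The simulations assume complete data, whereas the planned test is multiply imputed, so the adjusted model has not been tested exactly as it would be run. Changing a co-primary analysis also has a procedural price. SAP section 2 says an amendment will be considered, protocol 20.2 requires IRB approval for amendments, and SAP section 10 records that the agency rejected an earlier change to the lesion-count analysis.

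**Conclusion.** The concern holds, as an improvement worth making and not as a flaw in validity. Overall type I error is about 5% either way, and at 53.3% v 20.0% nothing changes. If the true effect is 12 to 15 points, the planned model's chance of passing depends on how severe patients fall between the arms: by about 5 points with few severe patients and a weak association, and by about 20 points with 35% severe and an odds ratio of 0.3. The baseline term largely removes that dependence, in both directions, so it guards against a lucky pass as well as an unlucky failure. The average power gain is small, 0 to 2.4 points.

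The sizes rest on an assumed severe share, odds ratio, center variation and complete data. The term deals with imbalance in baseline grade only.

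**What to change.** Before unblinding, add baseline IGA (3 v 4) as a factor in:
- the logistic regressions in SAP 8.7.1.2, 8.1.5.2 step 2 and 8.7.3;
- the GEE in 8.7.2.2, together with the model-based imputation there (class, var and diiga statements of the PROC MI code) and its analysis model;
- the IGA interaction models in 8.1.7.

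Match the text in SAP 8.1.4 (also correcting it for PAPSS), footnote d of Tables 14.2.1.2, 14.2.5.1 and 14.2.6.1, and footnotes d and g of Table 14.2.1.1. In the protocol, the same model stands in the synopsis, 19.4.2, 19.4.6, 19.4.7.2 and 19.4.8.2. Keep treatment plus center as a sensitivity analysis.

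The cost is one degree of freedom, these edits, and a decision on whether a protocol amendment and agency contact are needed. The odds ratio becomes conditional on baseline grade. Table 14.2.1.2 would show an adjusted p-value beside unadjusted percentages, so its footnote should say so. After unblinding, the same change would be post hoc.
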